5.0 Study Procedures

AIM 1. Explore MRSA abscess outcomes important to patients and their families through a Patient Advisory Board (PAB) and incorporate results in outcomes tools to be used in the randomized comparative effectiveness trial

In order to ensure we are measuring outcomes that are important to patients and their parents we will invite families who have experienced an incision and drainage procedure in the pediatric surgery clinic or Emergency Department to participate in a Patient Advisory Board (PAB) for the study. The Patient Advisory Board meetings will consist of informal and interactive discussions facilitated by design researchers. The meetings will allow participants to contribute as much or as little as they feel comfortable doing. One Patient Advisory Board will be comprised of parents or legal guardians of children ages 3 months to 8 years old who have undergone an incision and drainage procedure at Riley for an abscess. The other Patient Advisory Board will be made up of children 9-18 years old who have undergone an incision and drainage procedure at Riley for an abscess and their parents or legal guardians. The meetings will last up to 4 hours and will focus on study acceptability, recruitment, and patient centered outcomes. Participants will be compensated for their contribution to the study with a \$20 per hour payment in the form of a gift card. No more than two family members will be compensated for participation, e.g. one parent and one child who participate can each be paid \$20 per hour or two parents who participate can each be paid \$20 per hour. The Patient Advisory Board may also reconvene if additional patient input is needed during the study.

AIM 2: Compare strategies of care for MRSA SSTI, specifically abscess surgery and hygiene education versus abscess surgery and hygiene education followed by decolonization, on outcomes such as SSTI recurrence and repeated surgery, and patient-centered outcomes such as quality of life, side-effects and school absence

This part of our study is a randomized comparative effectiveness trial. Recruitment, randomization, and collection of outcomes will be done by PResNet.

The interventions will be targeted to all household members for whom consent can be obtained. All participants will receive written instructions for the intervention to which they are randomized. A registered nurse in the pediatric surgery clinic will be available to review instructions and answer any questions about MRSA. The instructions for the diluted bleach bath and Mupirocin administration will also be publically available in an online video.

Intervention number 1, Hygiene education

Participants will receive specific hygiene instructions according to existing recommendations from the Ryan White Center for Pediatric Infectious Disease, Riley Hospital as outlined here:

- Take daily showers or bath with soap
- Clean hands with soap and water or with hand sanitizers when hands are dirty, and after each bathroom break or diaper change
- Don't share towels, wash cloths, clothing, toothbrushes, or razors within the family or with friends
- Discard lotions in jars (can be easily contaminated with MRSA when someone puts their hand in a jar)
- Keep all wounds including cuts and scrapes clean and covered until healed
- Avoid other person's dirty bandages or uncovered wounds
- Encourage athletes or health club members to shower before and after all practices and competitions, and wipe down equipment surfaces before and after use
- Uniforms and practice jerseys should be washed after each game or practice. Sports equipment should be washed/cleaned weekly
- Wash all towels, wash cloths, sleepwear, underwear, and linens in hot water with laundry detergent once weekly and dry with hot air in a dryer

Intervention number 2, Hygiene education and Decolonization

Participants in this intervention group will receive the same hygiene instructions as the participants in the first intervention group. In addition, intervention number 2 will include the following for all consented household members:

- Twice weekly 15 minute soaks in diluted bleach water (a cup of 6% sodium hypochlorite [Clorox; The Clorox Company] for a standard 50 gallon tub of water, or a teaspoon for each gallon of water used) for the duration of 6 weeks
- Application of 2% mupirocin ointment by the use of clean swab to the bilateral anterior nares twice daily for ten days

At the time of enrollment, those randomized to intervention 1 will receive written hygiene instructions and a form to document outcomes, such as missed school or work. Those randomized to (or placed in) intervention 2 will receive a "kit", which will include a bucket for measuring the water, two cups to be used for measuring bleach, Clorox bleach, mupirocin ointment, double sided q-tips for application of mupirocin, hygiene instructions, as well as a form to document outcomes. Participants will also receive a link to an online video demonstrating the accurate process for preparing the diluted bleach bath and administering the mupirocin. (www.youtube.com/watch?v=3RbtyLT071M&feature=youtu.be) For each intervention arm, the above materials will be sent via mail after enrollment or provided in person by a research assistant.

Outcomes Measures

The patient-centered outcomes we plan to measure are summarized below.

The results of PAB sessions performed during aim 1 of this study will further inform some of the patient-centered outcomes measures.

Recurrence of SSTI

 Percent of participants with recurrence of skin and soft tissue infection by parental report at 6 weeks, 6 months and 12 months.
Repeat surgery

 Percent of participants with repeat incision and drainage procedure by parental report at 6 weeks, 6 months and 12 months.
Adherence to intervention

 Participant adherence to intervention measured on a 5 point scale by parental report at 6 weeks Household adherence measured on a 5 point scale by parental report at 6 weeks Have you tried anything outside the protocol to reduce the risk of MRSA recurrence? If yes, then what? (6 weeks)
Side effects
Percent of participants with side effects from intervention by parental report at 6 weeks and 6 months.
Participant time committed to intervention
Estimated weekly time to adhere to intervention by parental report at 6 weeks
Quality of Life

 Participants' quality of life measured by parent-proxy report (or youth tool) of the PedsQL 4.0 (Pediatric Quality of Life Inventory) at recruitment, 6 weeks, 6 months, and 12 months. Impact on free time measured on a 5 point scale by participant (age\geq13) and parental report at 6 weeks
Impact on school attendance

 Participants' school attendance by parental report at 6 weeks, 6 months and 12 months
Impact on parents' work attendance

 Assessment of parents' work attendance by self report at 6 weeks, 6 months and 12 months
Other Patient Centered Outcomes

 Participant's level of pain and discomfort at incision site via NRS at enrollment and 6 weeks. Participant's level of knowledge on what MRSA is and how to prevent its recurrence at enrollment, 6 weeks, 6 months, and 12 months. Additional measures as suggested by Aim 1

Data Collection and Study Tools

In order to evaluate the outcomes identified above, data will be collected by RAs in person or by phone at enrollment, and through phone interviews at approximately 6 weeks, 6 months and 12 months as time allows within the study period. RAs will be trained to perform phone interviews to assess recurrence, adherence, side effects, quality of life and school/work attendance. When requested by the participant, data collection tools/questions may be mailed via US post and/or emailed via secure link to REDCap. For all practical outcomes, such as missed school and work, participants will have forms to help them document these outcomes to aid in recollection at follow up.

The data collection for specific outcomes is outlined below:

Recurrence of skin and soft tissue infection

An RA will contact a parent of participants by phone at approximately 6 weeks, 6 months and 12 months. Participants will be asked whether they have had a recurrence of MRSA SSTI since the previous contact. If the answer is yes, they will also be asked if and where medical care was sought, and if any interventions (surgery, antibiotics) were needed. In cases for which antibiotics were prescribed, the name of antibiotics and duration of course will be recorded.

Repeat surgery

In a continuation of the questioning as shown above, an RA will contact a parent of participants by phone at approximately 6 weeks, 6 months and 12 months. They will be asked whether participants needed another incision and drainage procedure for MRSA SSTI in the same or another body location. If the answer is yes, they will also be asked in what facility that was done and whether antibiotics was prescribed or not. In the cases for which antibiotics were prescribed, the name of antibiotics and duration of course will be recorded.

Adherence to intervention

An RA will contact a parent of participants by phone at approximately 6 weeks after study randomization. The RA will ask parents of participants about adherence to interventions. The RA will initiate the conversations by saying “we are very interested to know what people think about the protocol”. For any of the interventions experienced (hygiene measures, mupirocin to nose, and bleach bath) participants will then be asked to report adherence. Adherence will be reported on a 5 point scale for child and other family members: We followed the instructions as recommended – always, sometimes, never.

For the purpose of analysis “always”, “never omitted more than one time/dose/bath in a row” and “never omitted more than one day/week in a row” will be considered adherent to treatment.

RAs will also ask: “Have you tried anything outside the protocol to reduce the risk of MRSA recurrence? If yes, then what?” This should capture any patients in the control arm who may be using decolonization regimens outside their designed protocol.

Side effects

An RA will contact a parent of participants by phone at approximately 6 weeks after randomization. The RA will ask parents of participants about side effects to interventions, for example: “Did any family member experience side-effects from the intervention? All parents will also be asked: “Dry skin and irritation in the nose or runny nose are sometimes reported in families, have any of your family members experienced those symptoms?”

Participant time committed to intervention

An RA will contact a parent of participants by phone at approximately 6 weeks after randomization. If participant report that they adhere to the protocol, the RA will ask parents to estimate the amount of time (in hours) per week they estimate the intervention took for all family members combined.

Quality of Life

Impact on quality of life will be measured by the use of Peds QL, Pediatric Quality of Life Inventory.²² The Peds QL was developed to measure health-related quality of life (HRQOL) in healthy children and adolescents and those with acute and chronic health conditions. The RA will administer the 23-item parent proxy report of the Pediatric Quality of Life Inventory in person or by phone at recruitment and at recruitment, and over the phone at approximately 6 weeks, 6 months, and 12 months. Participants 13 and older will be able to give self-report.

We will also assess the impact of the protocol on free time. RAs will ask participants (13yrs and older) “How much has the diagnosis of MRSA impacted your ability to do the things you like to do in your free time?”

Impact on school attendance

An RA will contact a parent of participants by phone at approximately 6 weeks, 6 months and 12 months. Parents of participants will be asked whether their child have missed any school days due to MRSA SSTI. Parents will be asked about number of school days missed.

Impact on parents' work attendance

An RA will contact a parent of participants by phone at approximately 6 weeks, 6 months and 12 months. Parents of participants will be asked whether they have missed any workdays due to their child's or their own MRSA SSTI. Parents will be asked about number of work days missed.

Medical data that cannot be collected directly from the parent of the patient, such as infection site, size of boil, location of reoccurrence may be collected via review of medical record.

Study Timeline

	Year 1				Year 2				Year 3			
	Qtr 1	Qtr 2	Qtr 3	Qtr 4	Qtr 1	Qtr 2	Qtr 3	Qtr 4	Qtr 1	Qtr 2	Qtr 3	Qtr 4
Aim 1 – PAB Sessions												
Aim 2 – Recruitment												
Aim 2 – Data Collection												
Statistical Analysis												
Manuscript Preparation												

6.0 Reporting of Adverse Events or Unanticipated Problems Involving Risk to Participants or Others

Oversight for the conduct of the study will be provided by the study PI, [name], with input and advice from his mentorship panel. He will take primary responsibility for overseeing data collection and verification and review of cumulative adverse events. While adverse events are not anticipated, a process has been established for continuous review of data and patient safety. The PI and his study team (PResNet RA and PResNet Study Coordinator) will conduct quarterly review meetings of the data. Other members will be included in these meetings at the discretion of the PI. Quarterly meeting summaries will include the number of patients recruited, rate of recruitment refusal, and subject attrition. Additionally the research team will report (1) all causes of mortality and (2) morbidity (hospitalizations, ER visits, and other injuries/problems resulting from the study protocol). Any adverse events occurring will be documented and reported according to Human Research Protection Program (HRPP) at Indiana University policies and procedures. This (de-identified) summary may be submitted to the Patient Advisory Panel (PAB) of the Patient Engagement Core. Cumulative adverse events and study progress summary will be communicated to the IRB at the time of continuing review.

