In this study, we intend to compare two therapies for MRSA SSTI (abscess surgery and hygiene education compared to abscess surgery and hygiene education followed by decolonization) to determine which is the more effective treatment for MRSA SSTI. We will focus on patient-centered outcomes as described by the families of MRSA infected patients. Such outcomes are likely to include quality of life, side effects, and school and work attendance. The hypothesis is that treatment with decolonization will decrease the rate of SSTI recurrence and improve overall patient-centered outcomes. The rationale is that negative outcomes such as recurrence may be avoided through the use of readily available prevention strategies, however, it is important to determine how burdensome those prevention strategies are for patients and families.

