Sub Aim 2a) Compare the two interventions on rate of self-reported MRSA SSTI recurrence and repeat surgery over a 12 month follow-up period.

Sub Aim 2b) Compare the two interventions on patient-centered outcomes such as quality of life and school attendance as well as others informed by Aim 1 over a 12 months follow-up period.

Sub Aim 2c) Determine the burden and patient preferences regarding the decolonization protocol on families.

The proposed research will be conducted as a randomized controlled comparative effectiveness trial over three years. Aim 1 will be carried out over a six months period. For Aim 2, recruitment and randomization will be done over a period of approximately 12 months and will be followed by a 12 month long evaluation period. Interviews as well as recruitment and randomization will be carried out in the pediatric surgery outpatient clinic and over the phone for patients of the Emergency Department at Riley Hospital for Children in Indianapolis, IN. Evaluation will be done by trained research assistants through phone interviews (or data collection via US post and/or online via secure email link to REDCap) at approximately 6 weeks, 6 months, and 12 months.

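### Recurrence is called SSTI in some places and MRSA SSTI in others; the interview as described covers only MRSA SSTI and asks for no culture result, so the event being counted is not settled

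*Combined protocol and SAP*

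**What the plan says.** Two terms are used for recurrence.

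- **SSTI, no organism named.** The hypothesis in 1.0 is that "treatment with decolonization will decrease the rate of SSTI recurrence". Aim 2 in 5.0 compares the arms "on outcomes such as SSTI recurrence and repeated surgery". The outcome list in 5.0 gives "Percent of participants with recurrence of skin and soft tissue infection by parental report at 6 weeks, 6 months and 12 months" and "Percent of participants with repeat incision and drainage procedure by parental report at 6 weeks, 6 months and 12 months". Section 8.0 sets the sample size on a halving of SSTI recurrence at 12 months, from a control risk of 50% whose reference is an unfilled placeholder.
- **MRSA SSTI.** Sub Aim 2a in 2.0 reads "Compare the two interventions on rate of self-reported MRSA SSTI recurrence and repeat surgery over a 12 month follow-up period". In the data-collection part of 5.0 the recurrence question is "Participants will be asked whether they have had a recurrence of MRSA SSTI since the previous contact", and on repeat surgery "They will be asked whether participants needed another incision and drainage procedure for MRSA SSTI in the same or another body location".

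After a yes to the recurrence question, "they will also be asked if and where medical care was sought, and if any interventions (surgery, antibiotics) were needed"; the name and duration of any antibiotic are also recorded. Culture is not among the items. Later in 5.0, review of the medical record is permitted for medical data that the parent cannot supply. Its examples are infection site, boil size and location of recurrence. The only study swab described (4.0) serves to identify eligible patients in the Emergency Department.

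**The concern.** Section 1.0 itself says that methicillin-susceptible *S. aureus* causes similar disease, so any SSTI and MRSA SSTI are different events. To answer the question as described, the parent must first decide which organism was responsible.

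- A boil that was never cultured, or that the parent does not think was MRSA, gives a no. The items on care, surgery and antibiotics are then not asked.
- A non-MRSA boil that the parent assumes is MRSA gives a yes, and nothing in the interview would show the error.

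The same restriction applies to repeat drainage. At stake is what the trial's recurrence percentage measures, and whether it is the event to which the 50% planning risk refers. An organism or event that is not asked about during follow-up may not be recoverable later.

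**Working it through.** **1. What the interview can yield under each reading**

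- *Listed outcomes mean any SSTI and any drainage.* A lesion or drainage that the parent does not attribute to MRSA is answered no and triggers no further item. The two listed percentages then cannot be obtained from the interview as described.
- *Listed outcomes mean MRSA SSTI.* The question matches the outcome, but the classification is the parent's. For reported events the interview records where care was sought, so the optional record review could find a culture for some of them. It is not prompted for events answered no.

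**2. The plan's own sample size**

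Inputs from 8.0: Pe = 0.50, Pi = 0.25 (50% relative reduction), alpha 0.05, power 0.80 (printed as beta). Sidedness is not stated; two-sided reproduces the figure. The mean risk P̄ must be (Pe + Pi)/2 = 0.375; the printed minus sign does not reproduce 59.

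n = 2(1.96 + 0.8416)² × P̄(1 − P̄)/(Pe − Pi)² = 15.70 × 0.2344/0.0625 = 58.9, so 59 per arm, as stated.

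Power at n = 59 per arm = Φ{[|Pe − Pi|√n − 1.96√(2P̄(1 − P̄))]/√[Pe(1 − Pe) + Pi(1 − Pi)]} = Φ{(1.920 − 1.342)/0.661} = 0.809.

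Expected children with an event: 59 × (0.50 + 0.25) = 44.25.

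**3. Illustrations**

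The documents give no reporting accuracy. The values of s and q below are assumptions, equal in both arms.

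(a) 50% vs 25% means any SSTI, and a share s of affected children is reported. Observed risk = s × true risk; unrecorded children = 44.25 × (1 − s).

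| s | Observed risks | Unrecorded | Relative risk | Power at 59 | n per arm for 80% |
|---|---|---|---|---|---|
| 0.9 | 45% vs 22.5% | 4.4 | 0.50 | 74% | 70 |
| 0.8 | 40% vs 20% | 8.8 | 0.50 | 66% | 83 |
| 0.7 | 35% vs 17.5% | 13.3 | 0.50 | 58% | 100 |

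(b) 50% vs 25% means MRSA SSTI, and a share q of children without an MRSA recurrence is wrongly counted. Observed risk = p + q(1 − p); added children = 59 × q × (0.50 + 0.75).

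| q | Observed risks | Added | Relative risk | Power at 59 | n per arm for 80% |
|---|---|---|---|---|---|
| 0.05 | 52.5% vs 28.75% | 3.7 | 0.55 | 75% | 68 |
| 0.10 | 55% vs 32.5% | 7.4 | 0.59 | 70% | 77 |

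Case (b) depends on q being equal in both arms. If decolonization also halved the wrongly counted lesions (q = 0.10 in control, 0.05 with decolonization), the risks would be 55% and 0.25 + 0.05 × 0.75 = 28.75%, the relative risk 0.52 and power 83%. The loss in (b) would then vanish.

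(c) 50% vs 25% means MRSA SSTI and parents label it correctly: 81%, no loss.

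**The case against.** The best case for the plan is that SSTI is shorthand. Every index child has a culture-confirmed MRSA abscess (3.0), and Sub Aim 2a names self-reported MRSA SSTI. The outcome list is introduced as a summary, and the later text describes how those outcomes are collected, under a heading that says skin and soft tissue infection directly above the MRSA question. Read as summary and detail, the item yields the listed percentage. This is a fair reading. No sentence states it, however, and it still leaves parents to judge the organism.

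The plan also promises parental report and nowhere a culture-supported outcome, so the missing culture item contradicts nothing. That stands: asking for culture is an improvement in measurement, not the repair of a broken commitment.

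The questions appear in indirect speech and the questionnaire is not in the documents, so the real instrument may be broader. If it is, 5.0 should say so.

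A reader might go further and infer three things that the documents do not support:

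- *That the listed outcomes can never be recovered.* This follows only if they mean any SSTI and any drainage. For events that are reported, record review could supply some culture results; its list of examples is open and does not exclude culture.
- *That the 50% describes a different event from the one collected.* The unfilled reference shows only that the event is unspecified.
- *That the trial is underpowered.* Every reporting rate above is assumed, and case (c) has no loss.

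**Conclusion.** The concern holds as a conditional one. The plan uses two terms for the outcome that sets its sample size, and does not say whether they mean the same event. On the any-SSTI reading, the interview as described cannot produce the listed recurrence and repeat-drainage percentages. On the MRSA reading, it produces them from the parent's judgement of the organism, with culture evidence available for only some reported events.

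The effect on the result cannot be sized from the documents. The illustrations run from no loss to a power of 58%, and rest on the assumed reporting rates, the planned 50% vs 25%, and 59 analysed per arm. Under-reporting that is equal in both arms, as in (a), leaves the relative risk at 0.50 and costs precision. False counting, as in (b), also pulls the relative risk towards 1, less so if decolonization reduces non-MRSA lesions too. Reporting that differs between arms because parents know their allocation is a separate limitation, which neither reading resolves.

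The change should be made: it is cheap, and events that are not asked about may be lost for good.

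**What to change.** 1. In both arms, ask first whether the child has had any new boil, abscess or other skin infection since the last contact, and whether any repeat drainage was done, without limiting either question to MRSA.
2. For each report, keep the existing items on care, surgery and antibiotics. Add whether the lesion was cultured and the result (MRSA, other, not cultured, unknown), using the record review already allowed where records are available.
3. Name either any SSTI or MRSA SSTI as the main recurrence outcome and report the other as secondary. State in 8.0 which event the 50% describes. If MRSA SSTI is the main outcome, state in advance how a report without a culture is counted.
4. Use the chosen term consistently in 1.0, Sub Aim 2a in 2.0, Aim 2, the outcome list and the interview text in 5.0, and 8.0. Check the school and work absence items in 5.0, which are also limited to MRSA SSTI.

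**Cost.** Two reworded questions, two added items, recording by episode, and a slightly longer interview; no extra visit or swab. Culture results will be incomplete, particularly for care outside the study hospital, so a culture-confirmed count will be partial. If MRSA SSTI stays the main outcome, the rewording itself costs no power. If any SSTI becomes the main outcome while 50% vs 25% means MRSA SSTI, other lesions in an assumed 5% or 10% of children without an MRSA recurrence, equal in both arms, would lower power to about 75% or 70%, by the arithmetic of case (b).

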7.0 Study Withdrawal/Discontinuation

Participants are always free to discontinue any therapy if they find it intolerable at any time. Participants will be encouraged to contact PResNet RA should they decide to do so. At every follow up point, PResNet RAs will attempt to make contact using each phone number up to three times. If they cannot make contact at that point, they will attempt to contact them by email or physical mailing address if those are available. Should those measures fail, the patient will be considered lost to follow-up. When assessments begin, RAs will explain to parents how long the interview should take. If a parent has to interrupt and end an interview, RAs will attempt to schedule a follow-up appointment at which they can continue from where they left off. Should they not be able to re-contact that parent, that patient will be considered lost to follow-up, but that data which has been collected will be used.

Participants are also able to leave the PAB at any time.

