8.0 Statistical Considerations

Based on previous published studies we estimated the risk of recurrence in the hygiene education group to be 50%. REF We then determined our sample size to ensure adequate power to detect a 50% relative reduction in SSTI recurrence in the hygiene and decolonization group at 12 months ($\alpha = 0.05$ and $\beta = 0.8$). We used the formula for sample size calculation for dichotomous outcomes $((2(Z \alpha + Z \beta)^2 \times P(1-\underline{P})) / ((P_e - P_i)^2))$ where $\underline{P} = (P_e - P_i) / 2$, P_e is the expected proportion of events in hygiene intervention group, and P_i is the expected proportion of events in hygiene and decolonization group. We determined our needed sample size in each group in our study to be 59. Assuming a 20% drop-out rate at 6 weeks, and another

10% at each subsequent follow up, we will aim to enroll 95 households/adolescent-parent pairs in order to achieve a final study group size of 59 participants in each of our intervention groups.

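### The 12-month recurrence percent has no counting rule, and families placed without randomization are not kept out of the comparison: specify a 12-month cumulative risk by randomized arm

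*Combined protocol and SAP*

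**What the plan says.** - Section 8.0 sizes the trial to "detect a 50% relative reduction in SSTI recurrence in the hygiene and decolonization group at 12 months", from an assumed 50% in the hygiene arm.
- Section 5.0, Outcomes Measures, lists the outcome as "Percent of participants with recurrence of skin and soft tissue infection by parental report at 6 weeks, 6 months and 12 months".
- Section 5.0, Recurrence of skin and soft tissue infection, gives the question put to families: "Participants will be asked whether they have had a recurrence of MRSA SSTI since the previous contact".
- Section 2.0, Sub Aim 2a, is to "Compare the two interventions on rate of self-reported MRSA SSTI recurrence and repeat surgery over a 12 month follow-up period".
- On losses, section 8.0 reads "Assuming a 20% drop-out rate at 6 weeks, and another" 10% at each later follow-up, and then "we will aim to enroll 95 households/adolescent-parent pairs in order to achieve a final study group size of 59 participants" in each group.
- Section 7.0 tells staff what to try: "At every follow up point, PResNet RAs will attempt to make contact using each phone number up to three times". For a parent who breaks off an interview and cannot be reached again, it adds "that patient will be considered lost to follow-up, but that data which has been collected will be used".
- Section 4.0 allows families already using bleach baths, or intending to, to be put in the decolonization arm instead of being excluded. Section 5.0 repeats this where it describes the kits.

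Section 8.0 contains a sample size calculation and no analysis rule.

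**The concern.** Each answer covers one interval, so the 12-month answer alone is not the 12-month risk for which the trial is sized. To get from three interval answers to one 12-month percent, someone must decide whether earlier answers are carried forward, who is in the denominator, and what becomes of a child who was reached at 6 weeks or 6 months but not at 12 months. The plan leaves these decisions open, so they could be made after the results are seen, and they change the estimate.

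The second problem concerns the comparison itself. Families who chose bleach baths may differ from randomized families in motivation or recurrence history. If they are counted in the decolonization arm, that arm is no longer a randomized group.

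**Working it through.** **Sample size reproduced.** Inputs from section 8.0: 50% vs 25%, alpha 0.05 (taken as two-sided), 80% power (the printed beta of 0.8 read as power), and P taken as the mean of the two risks, 0.375. Then n = 2(1.96 + 0.8416)² × 0.375 × 0.625 / 0.25² = 58.87, which rounds up to 59 per group, as stated.

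**Who lacks a 12-month call.** With compounding losses, 0.80 reach 6 weeks, 0.80 × 0.90 = 0.72 reach 6 months and 0.72 × 0.90 = 0.648 reach 12 months. So 1 − 0.648 = 35.2% have no 12-month call. If drop-out is permanent, 0.80 − 0.648 = 15.2% were reached earlier and 20% never. Reading 95 as per arm, 76 are reached at least once, 61.6 complete, and 14.4 were reached earlier only.

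If families can return, the split changes. With contacts reached independently at 80%, 72% and 65%, 0.20 × 0.28 × 0.352 = 2% have no contact and about 33% have an earlier contact but no 12-month call.

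**What the open choices do.** Assumed: true 12-month risks of 50% and 25%, and two timings, since the documents give none. One is a constant hazard. The other is a hygiene-arm cumulative risk of 15%, 35% and 50% at the three contacts, with 6.5%, 16.4% and 25% under decolonization.

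Expected reported recurrences per arm under constant hazard:
- Hygiene: 61.56 × 0.50 from responders, plus 2.59 from children lost later, = 33.37.
- Decolonization: 61.56 × 0.25 + 1.17 = 16.56.

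Under the 15/35/50% timing:
- Hygiene: 30.78 + 7.6 × 0.15 + 6.84 × 0.35 = 34.31.
- Decolonization: 15.39 + 7.6 × 0.065 + 6.84 × 0.164 = 17.0.

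The percentages below follow from these counts. Power is from simulation (40,000 trials per case, 95 per arm).

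| Cumulative reading | Constant hazard | 15/35/50% timing | Power |
|---|---|---|---|
| Denominator 95, lost children counted recurrence-free | 35.1% vs 17.4%, difference 17.7 | 36.1% vs 17.9%, difference 18.2 | 80–82% |
| Denominator 76, ever reported | 43.9% vs 21.8%, difference 22.1 | 45.2% vs 22.4%, difference 22.8 | 84–85% |
| 12-month responders | 50% vs 25%, difference 25.0 | 50% vs 25%, difference 25.0 | 82–83% |
| Responders plus earlier reported recurrences | 52.0% vs 26.4%, difference 25.6 | 52.7% vs 26.9%, difference 25.8 | 85–86% |
| Life-table over the three intervals | 50% vs 25%, difference 25.0 | 50% vs 25%, difference 25.0 | 85–86% |

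If the losses are added instead of compounded (57 completers per arm), the formula gives 79.5% for responders. For the first row it gives 77.6% (constant hazard) to 82%.

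**Last interval taken alone.** Under constant hazard the risks are 1 − √0.5 = 29.3% and 1 − √0.75 = 13.4%, with 56% power at 59 per group. Under the 15/35/50% timing they are 1 − 0.50/0.65 = 23.1% and 10.3%, with 46% power. The cumulative 50% vs 25% has 81% at 59.

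**Loss that depends on recurrence.** If loss doubles after a reported recurrence, responders give 24.0–24.3 points with 79–80% power; the life-table stays at 25.0 with 85–86%. If loss also doubles for unreported recurrences, responders give 22.7–23.3 points (74–76%) and the life-table 23.3–23.6 (81%).

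**Like-for-like gain.** The responder figures in the table use a pooled test, while the life-table uses an unpooled standard error with null rejection of 5.5–5.6%. With an unpooled test, responders have 83.3% and 83.7% power against 86.2% and 85.5% for the life-table. The gains are 86.2 − 83.3 = 2.9 and 85.5 − 83.7 = 1.8 points.

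**The case against.** The best defence is that the intended measure can be inferred. Sub Aim 2a speaks of a 12-month follow-up period. Consecutive questions about the time since the last contact together cover the year, and a later call also covers a skipped one. The enrolment target is inflated to leave 59 per group, so the planning basis was evidently 12-month completers. Section 7.0 says collected data are used. A one-sentence counting rule would close the gap, and preferring a life-table type of estimate is partly a matter of taste.

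Much of this stands. The loss was planned for: 95 per arm leaves 61.6 completers. But a planning basis is not an analysis rule. The sentence on collected data concerns interrupted interviews and does not say how the data enter the percent. None of these texts gives a denominator.

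Four stronger readings are tempting, and the documents do not support them:
- **The trial has only 46–56% power.** This requires the last interval alone to be the outcome. The question is an interviewing instruction, and Sub Aim 2a points to a cumulative measure, so this is an unlikely worst case.
- **A responder analysis would be badly biased.** Even with loss doubled after recurrence, the difference moves by only about 1 to 2 points.
- **Many 12-month calls will be cut because they depend on the time available.** The planned calendar is 6 + about 12 + 12 = 30 of 36 months, which fits every call.
- **Placed families will certainly be analysed as randomized.** The plan does not say so. It only fails to keep them out, and gives no number of such families.

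**Conclusion.** The concern holds in a limited form. The outcome that drives the sample size has no rule for combining contacts, no denominator and no treatment of children without a 12-month call. The same data could yield a difference from about 18 to about 25 points (just under 26 if earlier reported recurrences are simply added to the responders). What is at stake is pre-specification of the estimand: with compounding losses, every cumulative reading keeps about 80% power or more, and the required 59 per group is unchanged.

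The handling of placed families is a separate reason to act, because counting them in one arm would bias the randomized comparison by an amount the documents do not allow one to estimate.

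The figures assume true risks of 50% and 25%, the two assumed timings, and 95 per arm. Section 8.0 does not say whether 95 is per arm or in total. If it is the total, about 95 × 0.648 / 2 = 30.8 per arm would complete, with about 53% power among responders. The 15% and 20% shares also assume permanent drop-out.

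**What to change.** Add to section 8.0 a statement to this effect: the primary measure is the 12-month cumulative risk of first reported recurrence in the index child, compared by randomized arm. It is obtained from one interval-censored (Turnbull) estimate using the dates of contact, and every randomized child with at least one follow-up contact is included up to the last contact. The risk difference is reported with a 95% CI, for example by bootstrap. The estimate reduces to the life-table when no contact is skipped, so one named method serves both cases.

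State that families placed in the decolonization arm without randomization are left out of this comparison and reported separately.

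Report two sensitivity analyses: the percent among 12-month responders, and one that varies the recurrence risk in lost children, including those with no contact, over a stated range.

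**Cost.** The questions asked stay the same, the contact dates must be kept, and the analysis is slightly more work. The gain over responders is only about 2 to 3 power points under the planned drop-out. That figure is for the case without skipped contacts. For the interval-censored version with skips, the check covered coverage (0.950 and 0.935) and null rejection (0.046) in 1,000 trials, but not power. Children with no contact (20% under permanent drop-out) add no information, so this is not a full intention-to-treat analysis. Bias from recurrences that are never reported remains. Leaving out placed families reduces the number analysed, so they should not count towards the enrolment target for the randomized comparison.
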